6.1.4. Sensitivity Analysis of the Primary Efficacy Endpoint

No sensitivity analysis for the primary efficacy endpoint is planned.

6.1.6. Additional Analysis Supporting the Primary Efficacy Endpoint

Assessments for peripheral blood smear, which are used for response criteria for the primary efficacy endpoint will be summarized using:

- Baseline value
- Postbaseline maximum value

- Postbaseline minimum value
- Change and percentage change from baseline to postbaseline maximum value
- Change and percentage change from baseline to postbaseline minimum value

In addition, by-patient data listings will be provided.

6.2. Secondary Efficacy Endpoints

6.2.1. Definition of Secondary Efficacy Endpoints

The secondary efficacy endpoints are as follows:

- ORR (Cohorts 1 and 2): The ORR is the proportion of patients who achieve CR (CR_{MRD}- or CR_{MRD+/unk}), CRi, CRh, PR, or MLFS as determined by the investigator based on prespecified criteria (Appendix 2) while on study prior to initiation of any new anti-AML therapy (including SCT).
- CR/CRi Rate (Cohorts 1 and 2): The CR/CRi rate is the proportion of patients who achieve CR (CR_{MRD}- or CR_{MRD+/unk}) or CRi as determined by the investigator based on prespecified criteria (Appendix 2) while on study prior to initiation of any new anti-AML therapy (including SCT).
- CR_{MRD}– Rate (Cohorts 1 and 2): The CR_{MRD}– rate is the proportion of patients who achieve a CR_{MRD}– as determined by the investigator based on prespecified criteria (Appendix 2) while on study prior to initiation of any new anti-AML therapy (including SCT).
- CR/CRh Rate (Cohorts 1 and 2): The CR/CRh rate is the proportion of patients who achieve CR (CR_{MRD}- or CR_{MRD+/unk}) or CRh as determined by the investigator based on prespecified criteria (Appendix 2) while on study prior to initiation of any new anti-AML therapy (including SCT).
- cCR Rate (Cohorts 1 and 2): The cCR rate is the proportion of patients who achieve cCR determined by investigator based on the prespecified criteria (Appendix 2) while on study prior to initiation of any new anti-AML therapy (including SCT).
- DOR (Cohorts 1 and 2): The DOR is measured from the time assessment criteria are met for CR (CR_{MRD}- or CR_{MRD}-/_{unk}), CRi, CRh, PR, or MLFS, whichever is first recorded, until the first date of AML relapse, progressive disease, or death (including assessments post SCT). Those who are not observed to have a relapse, progressive disease, or death will be censored at the date of their last response assessment. If patients start taking new anti-AML therapies (except SCT and post SCT maintenance treatment) before relapse/PD/death, duration of response will be censored at the last response assessment before the initiation of the new anti-AML therapies.

- Duration of CR (Cohorts 1 and 2): The duration of CR is measured from the time the assessment criteria are first met for CR (CR_{MRD} or CR_{MRD+/unk}) until the first date of AML relapse or death (including assessments post SCT). Those who are not observed to have relapsed disease or death will be censored at the date of their last response assessment. If patients start taking new anti-AML therapies (except SCT and post SCT maintenance treatment) before relapse/death, duration of CR will be censored at the last response assessment before the initiation of the new anti-AML therapies.
- Duration of CR/CRi (Cohorts 1 and 2): The duration of CR/CRi is measured from the time the assessment criteria are first met for CR (CR_{MRD} or CR_{MRD}) or CRi until the first date of AML relapse or death (including assessments post SCT). Those who are not observed to have relapsed disease or death will be censored at the date of their last response assessment. If patients start taking new anti-AML therapies (except SCT and post SCT maintenance treatment) before relapse/death, duration of CR/CRi will be censored at the last response assessment before the initiation of the new anti-AML therapies.
- Duration of CR/CRh (Cohorts 1 and 2): The duration of CR/CRh is measured from the time the assessment criteria are first met for CR (CR_{MRD} or CR_{MRD+/unk}) or CRh until the first date of AML relapse or death (including assessments post SCT). Those who are not observed to have relapsed disease or death will be censored at the date of their last response assessment. If patients start taking new anti-AML therapies (except SCT and post SCT maintenance treatment) before relapse/death, duration of CR/CRh will be censored at the last response assessment before the initiation of the new anti-AML therapies.
- EFS (Cohorts 1 and 2): EFS is defined as the time from the date of the first dose of study treatment to the earliest date of documented relapse from CR, treatment failure (TF) defined as failure to achieve CR during the response assessment window (the first treatment dosing date until before the fifth cycle of magrolimab+venetoclax+azacitidine in Cohort 1 and the first treatment dosing date until before the third cycle of magrolimab + MEC in Cohort 2), or death from any cause. Response assessments post SCT or new anti-AML therapies will be excluded from deriving treatment failure. Table 6-1 summarizes the details of the EFS derivation algorithm.

Table 6-1. Censoring Rules for EFS

Situation		Event/Censored	Event/Censored Date
Achieved CR within the	No relapse or death	Censored	Last assessment date
response assessment window*	Had relapse or death	Event (Relapse/death)	Relapse date or death date which occurs earlier
	Had progression, death or new anti-AML therapies within the window	Event (TF)	Day 1 of treatment
Within the response assessment window, had at least one post-baseline response assessment, but didn't	No progression, death or new anti-AML therapies within the window, and have been on study beyond the up limit of the window	Event (TF)	Day 1 of treatment
achieve the CR	No progression, death or new anti-AML therapies within the window, and haven't been on study beyond the up limit of the window	Censored	Day 1 of treatment
Within the response assessment window, had no	Had death or new anti-AML therapies within the window	Event (TF)	Day 1 of treatment
post-baseline response assessment	No death or new anti-AML therapies within the window	Censored	Day 1 of treatment

^{*}Response assessment window: the first treatment dosing date to the fifth cycle of magrolimab+venetoclax+azacitidine in Cohort 1 and the first treatment dosing date to the third cycle of magrolimab + MEC in Cohort 2

- OS: The OS is measured from the date of the first dose of study treatment to the date of death from any cause. Those who are not observed to die during the study will be censored at last date they are known to be alive.
- RBC Transfusion Independence Rate: The RBC transfusion independence rate is the proportion of patients who have a 56-day or longer period with no RBC or whole blood transfusion at any time between the date of the first dose and discontinuation of study treatment among all patients who are RBC transfusion-dependent at baseline, defined as having received an RBC or whole blood transfusion within the 28 days prior to the first dose of study treatment (conversion rate), and among all patients who are RBC transfusion-independent at baseline (maintenance rate).
- Platelet Transfusion Independence Rate: The platelet transfusion independence rate is the proportion of patients who have a 56-day or longer period with no platelet transfusions at any time between the date of the first dose and discontinuation of study treatment among all patients who are platelet transfusion-dependent at baseline, defined as having received a platelet transfusion within the 28 days prior to the first dose of study treatment (conversion rate), and among all patients who are platelet transfusion independent at baseline (maintenance rate).

The date of the last known alive will be determined by selecting the last available visit date, including unscheduled visits, across all datasets.

Every attempt will be made to ensure that complete death dates are recorded. In those rare instances where complete death dates are not recorded, the following algorithm will be used:

- If day is missing but the month and year are available, then the imputed date will be the first day of the month or the last known alive date + 1, whichever is later.
- If day and month are missing but year is available, then the imputed date will be 01Jan of that year or the last known alive date + 1, whichever is later.

When the date of initiation of a new anti-AML therapy/SCT other than the study treatment is incomplete or missing, the following algorithm will be followed:

- If the day is missing but the month and year are available, then the imputed day will be the first day of the month or last dose date of study drug +1, whichever is later.
- If day and month are missing but year is available, then the imputed day and month will be 01Jan, first dose date of study drug +1, or the last day of the month for the last adequate disease assessment if they have the same year, whichever is later.

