3.1.2. Full Analysis Set

The Full Analysis Set (FAS) includes all enrolled patients who receive at least 1 dose of any study treatment, with treatment group designated according to the assigned treatment. This is the primary analysis set for efficacy analysis.

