6.2.2. Analysis Methods for Secondary Efficacy Endpoints

The point estimates of the ORR, CR rate, CR/CRi rate, CR_{MRD} rate, cCR rate, and CR/CRh rate and the corresponding 2-sided exact 95% CIs based on the Clopper-Pearson method will be provided for Cohorts 1 and 2. The analyses of RBC and platelet transfusion independence rates (conversion rate and maintenance rate) will be similar to those of ORR.

Medians, first quartile (Q1), and third quartile (Q3) of EFS distribution, and the proportion of patients who are event free at Weeks 12, 24, and 48 from the first dosing date will be estimated by cohort using the KM method and the corresponding 95% CIs will be reported. Kaplan-Meier plots will be provided. Analyses of OS will be similar to those of EFS.

For the time-to-event endpoints of duration of CR, duration of CR/CRi, duration of CR/CRh, DOR, analyses will be conducted on the subsets for which the outcome measures are defined. Specifically, the duration of CR, duration of CR/CRi, duration of CR/CRh, and DOR will be based on patients in Cohorts 1 and 2 who achieve CR, CR/CRi, CR/CRh, and OR, respectively. The KM method will be used to estimate median durations and 95% CIs, and KM plots will be provided.

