Assessment of leukemia response in patients with acute myeloid leukemia (AML) will be conducted based on the European Leukemia Net (ELN) 2017 recommendations for AML {Dohner 2017}, with modifications for the purposes of this protocol (protocol Appendix Table 10). Response classifications include complete remission without minimal residual disease (CR_{MRD-}), complete remission with positive or unknown minimal residual disease ($CR_{MRD+/unk}$), complete remission with incomplete hematologic recovery (CRi), morphologic leukemia-free state (MLFS), partial remission (PR), and stable disease (SD).

In addition, CR with partial hematologic recovery (CRh) will be assessed for AML, as defined as patients who achieve a CR per AML ELN 2017 recommendations {Dohner 2017}, but with only partial recovery of peripheral blood counts (platelets $> 50 \times 10^9$ /L and absolute neutrophil count ANC $> 0.5 \times 10^9$ /L).

Cytogenetic CR (cCR) will be assessed by 2003 IWG criteria as CR with normal cytogenetics (protocol Appendix Table 11) {Cheson 2003}.

The date of the bone marrow assessment should be used as the date of response assessment. Complete blood count results used for the response assessment will be derived from the best accompanying laboratory CBC result within the \pm 2-week window of the bone marrow assessment used to support the efficacy response assessment. All components (eg, platelets, absolute neutrophils) should come from the same test. If PD or relapse is assessed based on CBC assessments or new extramedullary disease, other than bone marrow blast assessments, then the date of the corresponding CBC or new extramedullary disease assessment date will be used as the date of response assessment.

Appendix Table 2. Response Criteria in Acute Myeloid Leukemia (Based on ELN 2017 Recommendations with Modifications)

	Definitions			
Response Criteria	Neutrophils	Platelets	Bone Marrow Blasts	Other
Complete remission without minimal residual disease (CR _{MRD})	> 1.0 × 10 ⁹ /L	> 100 × 10 ⁹ /L	< 5%	MRD negative (determined using multiparameter flow cytometry with a sensitivity of < 0.1%). Absence of circulating blasts and blasts with Auer rods; absence of extramedullary disease.

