Appendix Table 3. Additional Response Definitions Used in This Study (2003 IWG Criteria)

	Definitions			
Response Criteria	Neutrophils	Platelets	Bone Marrow Blasts	Other
Cytogenetic CR (cCR)	> 1.0 × 109/L	> 100 × 109/L	< 5%	Cytogenetics normal and no evidence of extramedullary disease

cCR = cytogenetic complete remission; CR = complete remission; IWG = International Working Group Source: {Cheson 2003}

Treatment Failure

Treatment failure is defined as failure to achieve complete remission or complete remission with incomplete hematologic recovery (CR) before the fifth cycle of magrolimab+venetoclax+azacitidine in Cohort 1 and before the third cycle of magrolimab + MEC in Cohort 2.

a Not in the ELN 2017 guidelines. Modification for the purpose of this protocol. A response could be classified as both CRh and CRi if both criteria are met.

GS-US-546-5920-Final-SAP-V3.0

ELECTRONIC SIGNATURES

Signed by	Meaning of Signature	Server Date (dd-MMM- yyyy hh:mm:ss)
PPD	Global Development Lead (GDL) eSigned	31-May-2024 16:34:25
PPD	Biostatistics eSigned	31-May-2024 20:55:31

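### The cCR rate counts patients who were cytogenetically normal at baseline alongside those who cleared an abnormality, so its meaning depends on the baseline karyotype mix

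*SAP*

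**What the plan says.** SAP Section 6.2.1 lists the cCR rate as a secondary endpoint for Cohorts 1 and 2: "The cCR rate is the proportion of patients who achieve cCR determined by investigator based on the prespecified criteria". The opening text of Appendix 2 gives the criterion: "Cytogenetic CR (cCR) will be assessed by 2003 IWG criteria as CR with normal cytogenetics". Appendix Table 3 repeats it with the count and blast thresholds for CR and adds "Cytogenetics normal and no evidence of extramedullary disease". All three places look only at the state at response.

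The denominator is the Full Analysis Set, of which Section 3.1.2 says "This is the primary analysis set for efficacy analysis". Section 6.2.2 gives the cCR rate a point estimate and says "the corresponding 2-sided exact 95% CIs based on the Clopper-Pearson method will be provided for Cohorts 1 and 2", naming no subset. Later in that section the duration endpoints are restricted: "analyses will be conducted on the subsets for which the outcome measures are defined". The cCR rate is not among them.

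Two other places might have resolved the question and do not. Section 3.4 rules out subgroup analyses by baseline characteristics. The estimand table in Appendix 1 lists CR, MRD-negative CR, CR+CRi, CR+CRh and ORR, but not cCR.

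**The concern.** Some patients may already have normal cytogenetics when they enter. Such a patient who reaches CR with a result that is still normal satisfies every element of the written criterion, although no abnormality has disappeared. The rate therefore adds together two outcomes: CR in patients with nothing to clear, and CR with clearance in patients who had an abnormality. How much each contributes depends on who was enrolled as well as on treatment effect.

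The SAP handles the same structure differently for transfusion independence, where a patient can also start in the target state. Section 6.2.1 computes one rate "among all patients who are RBC transfusion-dependent at baseline" and a separate maintenance rate for those independent at baseline. The cCR rate has no such split, and no planned table would let a reader recover it. What is at stake is the interpretation of one secondary endpoint, and any comparison of it across the two cohorts or with outside data.

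**Working it through.** **The plan's own figures.** The SAP gives no figure for cCR. The nearest are the design CR rates in Section 1.3: 53% for Cohort 1 (N = 46) and 35% for Cohort 2 (N = 36), with stated powers of 83.6% and 83.1%. The one-sample normal approximation at 1-sided alpha 0.1 reproduces both (83.58% and 83.11%). These powers concern CR and do not bear on cCR; only the design CR rates are used below.

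**Notation.** f is the share of patients with normal cytogenetics at baseline. CRn and CRa are the CR rates in the baseline-normal and baseline-abnormal groups. c is the share of CRs in the abnormal group with a normal result at response. The documents give none of these by karyotype group. To keep the formulas short, every baseline-normal CR is taken to have a normal result at response.

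- Planned rate = f × CRn + (1 − f) × CRa × c
- Patients who cleared an abnormality, as a share of all patients = (1 − f) × CRa × c
- Rate among patients with a baseline abnormality = CRa × c

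**Comparison 1: share of all patients who cleared.** The planned rate exceeds this by f × CRn, which is never negative. With CRn = 35% and f = 30% to 50%, the excess is 0.30 × 35 = 10.5 to 0.50 × 35 = 17.5 points.

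**Comparison 2: rate among patients with an abnormality.** The difference is f × (CRn − CRa × c). With CRn = CRa = 35% it becomes f × 35 × (1 − c):

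| f | c | Planned rate | Rate among abnormal | Gap (points) | Share of cCR responders normal at baseline, f / [f + (1 − f)c] |
|---|---|---|---|---|---|
| 30% | 70% | 35 × 0.79 = 27.65% | 24.5% | 3.15 | 38% |
| 50% | 70% | 35 × 0.85 = 29.75% | 24.5% | 5.25 | 59% |
| 30% | 50% | 35 × 0.65 = 22.75% | 17.5% | 5.25 | 46% |
| 50% | 50% | 35 × 0.75 = 26.25% | 17.5% | 8.75 | 67% |

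At the Cohort 1 design rate of 53%, the same grid gives gaps from 0.30 × 53 × 0.30 = 4.8 to 0.50 × 53 × 0.50 = 13.3 points. If every CR clears (c = 100%), the gap is zero.

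**Can the sign change?** Yes, when CRn is below CRa × c. With f = 40%, CRn = 30%, CRa = 60% and c = 70%, the planned rate is 0.40 × 30 + 0.60 × 60 × 0.70 = 37.2%, against 60 × 0.70 = 42.0%.

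**Precision.** Take an illustrative Cohort 2 of 36 patients: 14 normal at baseline, of whom 5 count as cCR, and 22 abnormal, of whom 4 clear. The planned rate is 9/36 = 25.0% (exact 95% CI 12.1% to 42.2%). Among abnormal patients it is 4/22 = 18.2% (5.2% to 40.3%).

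**The case against.** A reader might infer that the cCR rate overstates cytogenetic remission as a matter of fact, or that a baseline-normal patient qualifies merely by reaching CR. The SAP supports neither. A normal result at response is still required, so a CR with no follow-up cytogenetics or with a new abnormality does not count. Section 1.2 says only that marrow samples may be used for cytogenetics, so missing results are possible and would pull the rate down. The karyotype mix and the clearance share appear nowhere in the SAP, and the direction against abnormal-karyotype patients can reverse, as shown above. It would also go too far to say that the rate largely repeats CR: the table gives 22.75% to 29.75% against a CR rate of 35%.

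Other points on that side also stand. The SAP's statements of the criterion agree with each other and never call the endpoint clearance. Appendix 2 refers to a protocol table that is not at hand and might add a restriction. The endpoint is untested in a proof-of-concept study, and the gaps are small beside the intervals. Section 2.2 reports the primary analysis as already conducted, so replacing the denominator now would be a post hoc redefinition.

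None of this removes the central point. As reproduced in the SAP, the criterion has no baseline condition, the rate runs over all treated patients, and nothing planned separates the two kinds of responder. A patient-level response criterion does not settle the denominator of a rate; the SAP does that.

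**Conclusion.** The point holds as a matter of definition: the planned cCR rate combines CR in baseline-normal patients with clearance in the others, and varies with the baseline mix. Read as the share of all patients who cleared an abnormality, it cannot be too low on this account, though missing follow-up results could lower it for a different reason. Against patients with a baseline abnormality, it is too high if CR rates are similar in the two groups and not every CR clears. That is about 3 to 9 points at CR 35%, with 30% to 50% normal at baseline and 50% to 70% clearance, all of them assumptions. It can be too low if baseline-normal patients have a much lower CR rate. The consequence is limited to how a secondary endpoint is read; the primary CR test does not change.

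**What to change.** In Sections 6.2.1 and 6.2.2, keep the planned all-patient cCR rate and add beside it the rate with Clopper-Pearson CI among Full Analysis Set patients with abnormal baseline cytogenetics. State that patients without post-baseline cytogenetics count as non-responders. Show the numbers of patients and of cCR responders with normal and with unknown baseline cytogenetics. Because the primary analysis has already been run, label the addition as supportive.

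The cost is a baseline cytogenetics flag, a sentence or two of text and one more table row with counts. The added estimate has a smaller denominator: with 30% to 50% normal at baseline, about 18 to 25 of the 36 patients planned for Cohort 2, and so a wider interval. The number for Cohort 1 cannot be stated, because Section 6.4 says its enrollment ended early and below the planned size.

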12. SOFTWARE

SAS® Software Version 9.4. SAS Institute Inc., Cary, NC, USA.

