Appendix Table 1. List of Estimands and Estimators of Main Analyses

Treatments	Variable (Endpoint)	Intercurrent Events & Strategies	Population Level Summary	Estimators
magrolimab + venetoclax + azacitidine, magrolimab + MEC	OS	 Discontinuation of treatment: treatment policy SCT, New anti-cancer therapy: treatment policy 	Kaplan-Meier estimates (medians, Q1, and Q3 of OS distribution, and the proportion of patients who are event free at Weeks 24, 48, and 96 from the first dosing date)	Main Estimator: median OS and 95% CI for each cohort.
magrolimab + venetoclax + azacitidine, magrolimab + MEC	EFS	 Discontinuation of treatment: treatment policy Death, Treatment failure: composite SCT, New anti-cancer therapy: treatment policy 	Kaplan-Meier estimates (medians, Q1, and Q3 of EFS distribution, and the proportion of patients who are event free at Weeks 12, 24, and 48 from the first dosing date)	Main Estimator: median EFS and 95% CI for each cohort.
magrolimab + venetoclax + azacitidine, magrolimab + MEC	CR rate / CR _{MRD} - rate / rate of CR+CRi / rate of CR+CRh/ ORR	 Discontinuation of treatment: treatment policy SCT, New anti-cancer therapy: while-on-treatment Loss to follow-up: while-on-treatment 	Point estimates of the rate and the corresponding 2-sided exact 95% CIs	Main Estimator: Estimate rate and CIs based on the Clopper-Pearson method for each cohort; Test rate against the historical control rate using 1-group Chi-square test for each cohort separately.
magrolimab + venetoclax + azacitidine, magrolimab + MEC	RBC/platelet transfusion independence	 Discontinuation of treatment: while-on-treatment Dose reduction or temporary delay: treatment policy Loss to follow-up: while-on-treatment 	Point estimates of the rate and the corresponding 2-sided exact 95% CIs	Main Estimator: Estimate rate and CIs based on the Clopper-Pearson method for each cohort.

Appendix 2. Disease Response Criteria Based on European Leukemia Net (ELN) and International Working Group (IWG) Criteria

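### Table 6-1 censors two groups without CR at Day 1, where every treatment failure is also dated, so the Kaplan-Meier EFS curve treats them as if they had reached CR

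*SAP*

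**What the plan says.** SAP Section 6.2.1 counts three things as EFS events: relapse from CR, death from any cause, and "treatment failure (TF) defined as failure to achieve CR during the response assessment window". The window runs to Cycle 5 in Cohort 1 and Cycle 3 in Cohort 2.

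Table 6-1 then sets the dates. All three treatment-failure rows are events at "Day 1 of treatment". Two rows for patients without CR are censored at that same date:

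- Row A, assessed after baseline: "No progression, death or new anti-AML therapies within the window, and haven't been on study beyond the up limit of the window".
- Row B, never assessed after baseline: "No death or new anti-AML therapies within the window". This row sets no condition on length of follow-up.

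Only patients with CR inside the window have an EFS time beyond Day 1. Their event date is "Relapse date or death date which occurs earlier"; without an event they are censored at the last assessment.

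Section 6.2.2 names Kaplan-Meier as the method for the median, quartiles and landmarks; of the last it says "the proportion of patients who are event free at Weeks 12, 24, and 48 from the first dosing date will be estimated by cohort using" that method. Appendix Table 1 gives "Main Estimator: median EFS and 95% CI for each cohort". Section 12 names "SAS® Software Version 9.4" and the SAP states no special rule for ties. No sensitivity analysis of EFS is described.

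**The concern.** Censoring is harmless only if the censored patient leaves the risk set before the events that would otherwise be credited to others. Here the censoring time and the failure time are the same day. Kaplan-Meier by convention processes events before censorings at a tied time, so rows A and B stand in the Day 1 denominator as patients who did not fail. Their weight then passes to the CR patients for the rest of the curve.

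Row B has a second problem. A never-assessed patient who remains on study past the window has not achieved CR in it, and one who dies after the window has died. Section 6.2.1 makes both events, and Appendix Table 1 treats death and treatment failure as composite. Table 6-1 censors both patients at Day 1 and discards what was observed.

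The same patients count as non-responders in the CR rate on the Full Analysis Set (Sections 3.1.2, 6.1.1 and 6.1.3). The two endpoints would therefore treat them in opposite ways, and the EFS error runs in the favourable direction.

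**Working it through.** The SAP states no EFS estimate, event count or EFS power, so there is no figure to reproduce. The N and CR rate used below for illustration come from Section 1.3, and the Cohort 2 power there was checked first: Φ([(0.35 − 0.19)√36 − 1.2816√(0.19 × 0.81)] / √(0.35 × 0.65)) = 0.831, which agrees with the stated 83.1%.

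**Inputs**

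- N = 36, the Cohort 2 planned total.
- CR = 13, from 0.35 × 36 = 12.6, rounded. This is an assumption, not a result.
- m = patients censored at Day 1 under rows A and B. The SAP does not give it; 2, 4 and 6 are assumed.
- TF = N − CR − m, all dated Day 1.

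**Formulas**

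- SAP rule: S(Day 1) = 1 − TF/N = (CR + m)/N. This is the value that would result if all m had reached CR.
- Unknowns left out: CR/(CR + TF) = CR/(N − m).
- Unknowns counted as failures: CR/N.
- After Day 1: S(t) = S(Day 1) × S_CR(t), where S_CR is the curve among CR patients. Weeks 12, 24 and 48 therefore carry the same ratio as Day 1.

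**Results, N = 36 and 13 CR**

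| m | TF | SAP rule | Left out | As failures | SAP ÷ left out | SAP ÷ failures |
|---|---|---|---|---|---|---|
| 2 | 21 | 15/36 = 0.417 | 13/34 = 0.382 | 13/36 = 0.361 | 1.09 | 1.15 |
| 4 | 19 | 17/36 = 0.472 | 13/32 = 0.406 | 0.361 | 1.16 | 1.31 |
| 6 | 17 | 19/36 = 0.528 | 13/30 = 0.433 | 0.361 | 1.22 | 1.46 |

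Each additional patient in rows A or B adds 1/36 = 2.8 percentage points at Day 1 relative to counting that patient as a failure. Coding the product-limit estimator directly gave the same SAP-rule and as-failures values as the closed form.

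**Median.** It stays at Day 1 while S(Day 1) is below 0.5, which holds for m up to 4. At m = 5 the value is 18/36 = 0.500, the boundary. At m = 6 the median moves past Day 1 under the SAP rule but stays at Day 1 under both alternatives.

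**Cohort 1.** With the planned N = 46 and 24 CR (0.53 × 46 = 24.4) and m = 4, the three values are 28/46 = 0.609, 24/42 = 0.571 and 24/46 = 0.522. Section 6.4 says actual enrolment was smaller, so this shows direction only.

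**Would a later censoring date help?** No. Placing these patients' censoring at an assumed Day 28 gave the same values at Weeks 12, 24 and 48, because they still pass through the Day 1 drop as survivors.

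**The case against.** The strongest case on the other side concerns importance and size. EFS is one of many secondary endpoints. It has no comparator arm and no test. The only planned hypothesis test is the Cohort 2 CR rate against 19%, which Table 6-1 does not touch. That stands, and it limits the weight of the point.

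m may also be small. Table 6-1 already counts as failures the patients who die, progress or start new therapy in the window after an assessment, those who die or start new therapy in it without one, and assessed non-CR patients followed past it. The primary analysis waits for Week 24 (168 days) or study discontinuation (Section 2.2). That is later than four 28-day cycles (112 days), so administrative cutoff should not feed row A. Section 1.2 also generally calls for a response assessment at end of treatment, which limits row B. This is fair; the table above is illustrative.

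For row A, censoring incomplete observation does not in itself contradict the event definition, because a patient who leaves early was not observed to fail throughout the window. That also stands: the fault in row A is where the censoring falls. It does not rescue row B.

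Two stronger readings are tempting. A reader might infer that 36.1% is the true value and that all landmarks are 31% too high at m = 4. The documents do not support this. The CR status of these patients is unknown, 0.361 is what results if all of them fail, and leaving them out gives 0.406, an excess of 16%. A reader might also infer that the window test cannot be applied to someone who stops before Cycle 5 or Cycle 3. Sections 1.2 and 5.2.2.1 give a 28-day planned cycle, so a planned date can be derived. The SAP lacks precision here, but the test is not impossible.

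**Conclusion.** The rule is wrong as written and should be fixed. Whenever m and TF are both above zero, the EFS curve leaves Day 1 at (CR + m)/N and every later point is scaled up with it. There is no inflation only if all the censored patients would have reached CR. Row B in addition contradicts Section 6.2.1.

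The size is not known, because the SAP does not give m. In the assumed Cohort 2 case the excess for m = 2 to 6 is 9% to 22% relative to leaving the unknowns out, and 15% to 46% relative to counting them as failures. The main estimator, the median, is unaffected in that case for m up to 4. All this rests on the standard tie convention. If censorings were processed first, the estimate would be CR/(CR + TF), but the SAP does not specify that.

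It would be going too far to say that the trial's main conclusion is at risk. EFS is descriptive, and the CR rate analysis is untouched.

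**What to change.** In Table 6-1:

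- Make row B patients who were on study beyond the window, or who died later, Event (TF) at Day 1, as Section 6.2.1 requires.
- Count patients in either row who left before the window closed without CR as TF at Day 1 in the main analysis. This matches their handling as non-responders in the CR rate.
- Keep the current censoring rule as a labelled sensitivity analysis.
- Report by cohort the number censored at Day 1 under the current rule.
- State the upper limit of the window as a study day. On planned 28-day cycles, Cycle 5 starts on Day 4 × 28 + 1 = 113 and Cycle 3 on Day 2 × 28 + 1 = 57.

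Estimating the Day 1 step among evaluable patients only would also remove the artefact, but it would leave EFS and the CR rate on different footings.

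The cost is a table edit, a re-run of the EFS derivation and a less favourable curve. Section 2.2 reports the primary analysis as already done on data extracted on 18 October 2023, and Section 13 records the last EFS rule change on 17 October 2023. The new change must therefore be documented as made after the primary analysis.
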